#### **7.4.2 Dose Change of Study Therapy**

Dose change (interrupted, dose omission, delayed or discontinued) with associated reason will be listed for each subject and summarized by dose levels and overall or by treatment group for nivolumab/daratumumab cohorts. The number of subjects with infusion interruptions, reason for first interruption and duration of first interruption of study medication will be summarized by dose levels and overall or by treatment group for nivolumab/daratumumab cohorts. Dose delays and discontinuation (with associated reason, retrieved from CRF dosing pages) of study medication will be summarized.

[REDACTED]

[REDACTED]

#### **7.5 Efficacy**

The summary of efficacy measures will be grouped by treatment arm and dose level within each disease type and/or within each sub-disease type by histology.

Efficacy analyses will be performed for all treated subjects for the nivolumab monotherapy cohort, nivolumab/lirilumab cohort, nivolumab/ipilimumab cohort and all randomized MM subjects for nivolumab/daratumumab cohorts. The ORR, time to response, duration of response, PFSR, and PFS, as assessed by the IRRC (only for cHL subjects receiving nivolumab monotherapy) and the investigator will be analyzed. ORR in the nivolumab/daratumumab cohorts will be assessed by investigator only.

#### **Best Overall Response**

BOR outcomes will be tabulated. A frequency distribution of the BOR outcomes together with ORR with corresponding 2-sided 95% exact confidence interval will be tabulated.

### **Objective Response Rate**

The objective response rate (ORR) and corresponding two-sided 95% exact confidence interval will be provided by within each treatment cohort by disease type, and by treatment arm within each nivolumab/daratumumab cohorts based on the Clopper-Pearson method.

### **Duration of Response**

The median duration of response will be estimated by Kaplan-Meier methodology depending on data availability. The corresponding 95% confidence interval will be derived based on Greenwood formula and log-log transformation. The number of subjects still in response at the time of database lock will be indicated. If number of responders is small, the above analysis may not be performed. Duration of response will be listed.

### **Progression Free Survival**

Kaplan-Meier plots of PFS will be provided. PFS Rate at select time points will be estimated by Kaplan-Meier methodology, and the corresponding two-sided 95% confidence interval will be derived based on Greenwood formula depending on data availability.

### **Time to Response**

TTR will be derived and listed. TTR will be summarized in a swimmer plot. Time to best response will be derived and listed for nivolumab/daratumumab cohorts.

### **Tumor Measurements (Lymphoma)**

For lymphoma subjects, tumor measurements, target lesions tumor burden (the sum of the products of the greatest diameters) at each visit, along with corresponding percent change from baseline, will be listed.

Individual percent changes in the target lesion tumor burden over time may be presented graphically (a.k.a spider plot) (Hodgkin/PMBL, T-cell lymphoma, B-cell lymphoma) based on data availability within a disease type.

The individual maximum tumor reduction from baseline may be presented graphically (a.k.a waterfall plot) based on data availability within a disease type.

Spider plot and waterfall plot will exclude multiple myeloma and cutaneous T-cell Lymphoma patients.

Tumor measurements for subjects received treatment beyond progression will be listed.

### **Overall Survival**

Median overall survival and corresponding two-sided 95% confidence interval will be estimated by K-M method. Kaplan-Meier plots of OS will be provided.

### **Duration of Follow-up**

The descriptive median, minimum and maximum will be calculated for the duration of follow-up.

### **Serum and Urine M-Protein and serum Free Light Chain (Myeloma)**

Summary statistics for serum and urine test results, and corresponding changes (or percent changes) from baseline will be tabulated.

For patients with measurable disease in serum M-protein ( $\geq 0.5$  g/dL) and/or measurable disease in urine M-protein ( $\geq 200$  mg/24 hours), the individual percent changes in the M-protein over time will be presented graphically (a.k.a spider plot). If the disease is not measurable by either serum M-Protein ( $< 0.5$  g/dL) or urine M-protein ( $< 200$  mg/24 hours), the individual percent changes in the serum free light chain over time will be presented graphically (a.k.a spider plot).

### **FDG-PET Assessment (HL or PMBL)**

The number and percentage of subjects with PDG-PET scan performed will be summarized by visit for HL and PMBL subjects. Among subjects with PDG-PET scan performed, the number and percentage of subjects with abnormal findings will be summarized by visit.

All related data will be listed.

### **mSWAT Score**

To evaluate the response in skin for subjects with cutaneous T cell lymphoma, the percentage change from baseline on the mSWAT score will be derived and listed at subject level.

### **MRD (nivolumab-daratumumab)**

Analyses of MRD status will be based on all evaluable MRD subjects and performed at each sensitivity level. Both molecular and cytometry MRD status from bone marrow aspirate will be evaluated. MRD negativity status will be evaluated by timepoints. Summary statistics of time to the first MRD negativity will be provided by treatment group for subjects achieving MRD negative status. Cumulative MRD negativity rates will be tabulated at the first on-study assessment (i.e, C4D1 or  $\geq$ VGPR, whichever occurs first) and every 6 months thereafter depending on the data availability. Median duration of the MRD negativity and corresponding two-sided 95% CI will be analyzed by KM product limit method for subjects who achieved MRD negative status depending on the data availability. A plot of individual time course of abnormal bone marrow plasma cells will be produced.

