The planned sample size for Cohort B (ND, D) will be approximately 60 treated subjects, randomized in a 2:1 ratio in favor of the ND arm.

This is a Phase 1/2 study and the sample size in Cohort B is not powered for statistical hypothesis testing but is designed to evaluate both safety profile and clinical benefit of nivolumab with daratumumab.

If the true toxicities incidence rate in a cohort is 20% then with 20 patients in D cohort, there is 7% chance of observing 0 - 1 toxicities (false negative rate). If the true toxicities incidence rate in a cohort is 5% rather than 20%, then there is 26% chance that there will be at least 2 toxicities in 20 subjects (false positive rate). If the true toxicities incidence rate in a cohort is 20% then with 40 patients there is 3% chance of observing 0 - 3 toxicities (false negative rate). If the true toxicities incidence rate in a cohort is 5% rather than 20%, then there is 14% chance that there will be at least 4 toxicities in 40 subjects (false positive rate).

In 2 daratumumab monotherapy studies in relapsed/refractory MM patients, including a Phase 1/2 dose escalation study (GEN501)ⁱ in patients with at least 2 lines of prior therapy and a Phase 2 study (SIRIUS)ⁱⁱ in patients with at least 3 lines of prior therapy, the ORR were 36% and 29.2% respectively.

In two combination studies in relapsed/refractory MM patients with at least 2 lines of prior therapy, including a Phase 1b study of daratumumab in combination with pomalidomide and dexamethasoneⁱⁱⁱ and a Phase 1 dose-escalation study of pembrolizumab in combination with lenalidomide and dexamethasone,^{iv} the ORR were 60%.

Table 8.1-1 summarizes the 95% exact CI for the target ORRs ranging from 30% to 80% with sample size of 20 or 40 in a cohort. At observed ORR \geq 55% with 20 subjects, the lower bound of the 95% CI is 31.5%. At observed ORR \geq 77.5% with 40 subjects, the lower bound of the 95% CI is 61.5%.

Table 8.1-2 summarizes the 95% exact CI for the target MRD-target negativity rates ranging from 10% to 30% with sample size of 20 or 40 in a cohort. At observed MRD-target negativity rates \geq 30% with 20 subjects and observed MRD-target negativity rates \geq 20% with 40 subjects, the lower bound of the 95% CI are 11.9% and 9.1% respectively compares favorably to historical MRD-target negativity rate of 8% in recurrent pretreated relapsed or refractory MM.

Endpoints:

Safety:

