### Objective Response Rate (ORR)

Objective response rate is defined as the proportion of subjects whose BOR is one of the following responses divided by the number of treated subjects or number of randomized subjects in nivolumab/daratumumab cohort.

- for lymphoma subjects whose BOR is either complete remission or partial remission
- for myeloma subjects whose BOR is stringent complete response, complete response, very good partial response, or partial response

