### **Minimal Residual Disease (MRD)**

In the nivolumab/daratumumab cohorts, MRD from bone marrow aspirate will be evaluated. MRD will be assessed by Next Generational Flow Cytometry (NGF) and Next Generational Sequencing (NGS).

The timepoint MRD negativity status is a dichotomized variable for quantifiable MRD detection. MRD negativity status will be considered at  $10^{-5}$ , as per IMWG guidelines; other sensitivity levels such as  $10^{-4}$  and  $10^{-6}$  will also be considered.

The first MRD negative status is defined as the first negative status designation over the study as a whole, recorded between the date of first dose and the date of objectively documented progression or the date of subsequent therapy, whichever occurs first.

The best MRD negative status is defined as the best status designation with the lowest sensitivity level over the study as a whole, recorded between the date of first dose and the date of objectively documented progression or the date of subsequent therapy, whichever occurs first.

Time to the first MRD negative status is defined as the time from the date of randomization to the date of the first MRD negative status.

The duration of the MRD negativity is defined as the time between the date of first MRD negativity to the date of the first MRD positivity, or the date of the first objectively documented progression as assessed according to IMWG criteria or death due to any cause whichever is earlier prior to the initiation of subsequent anti-cancer therapy. Subjects who didn't have MRD positivity, and didn't progress nor die will be censored on the date of their last MRD negativity prior to the initiation of subsequent anti-cancer therapy.

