## NIVOLUMAB/DARATUMUMAB COHORTS

Cohort A (ND ± Pd) is closed to enrollment.

The planned sample size for Cohort B (ND, D) will be approximately 60 treated subjects, randomized in a 2:1 ratio to the ND and D arms, respectively. The sample size is not powered for statistical hypothesis testing, but designed to evaluate both the safety profile and clinical benefit of nivolumab in combination with daratumumab.

If the true toxicities incidence rate in a cohort is 20% then with 20 patients in the D cohort there is a 7% chance of observing 0 - 1 toxicities (false negative rate). If the true toxicities incidence rate in a cohort is 5% rather than 20%, then there is 26% chance that there will be at least 2 toxicities in 20 subjects (false positive rate). If the true toxicities incidence rate in a cohort is 20% then with 40 patients in ND cohort there is 3% chance of observing 0 - 3 toxicities (false negative rate). If the true toxicities incidence rate in a cohort is 5% rather than 20%, then there is 14% chance that there will be at least 4 toxicities in 40 subjects (false positive rate).

In two daratumumab monotherapy studies in relapsed/refractory MM patients, including a Phase 1/2 dose escalation study (GEN501) in patients with at least 2 lines of prior therapy and a Phase 2 study (SIRIUS) in patients with at least 3 lines of prior therapy, the ORR were 36% and 29.2% respectively. In two combination studies in relapsed/refractory MM patients with at least 2 lines of prior therapy, including a Phase 1b study of daratumumab in combination with pomalidomide and dexamethasone and a Phase 1 dose-escalation study of pembrolizumab in combination with pomalidomide and dexamethasone, the ORR were 60%. At observed ORR  $\geq$

55% with 20 subjects, the lower bound of the 95% CI exceeds 31.5%. At observed ORR  $\geq 77.5\%$  with 40 subjects, the lower bound of the 95% CI exceeds 61.5%.

At observed MRD negative rate  $\geq 30\%$  with 20 subjects and observed MRD-target negativity rates  $\geq 20\%$  with 40 subjects, the lower bound of the 95% CI are 11.9% and 9.1% respectively, compares favorably to historical MRD-target negativity rate of 8% in the target population.

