### 6.3 Populations for Analyses

- All Enrolled Subjects: All subjects who sign informed consent form and were registered in IVRS.
- All Randomized MM subjects: All enrolled MM subjects who were randomized to one of nivolumab and daratumumab cohorts.
- All Treated Subjects: All subjects who signed informed consent and received at least one dose of study medication are considered treated and are included in the treated population
- Pharmacokinetic (PK) Population: All subjects who receive at least one dose of study medication and have available serum concentration data.
- Response Evaluable Subjects: All treated subjects with measurable disease at baseline and one of the following: 1) at least one on-treatment efficacy assessment, 2) clinical progression, or 3) death.
- Immunogenicity evaluable subjects:
  - Nivolumab ADA Evaluable Subjects: all treated subjects with baseline and at least 1 postbaseline nivolumab immunogenicity assessment.
  - Ipilimumab ADA Evaluable Subjects: all treated subjects with baseline and at least 1 postbaseline Ipilimumab immunogenicity assessment.
  - Lirilumab ADA Evaluable Subjects: all treated subjects with baseline and at least 1 postbaseline Lirilumab immunogenicity assessment.
- All Treated PD-L1 Evaluable Subjects: All treated subjects with quantifiable PD-L1 expression (ie excludes indeterminate and unknown).
- All MRD Evaluable Subjects: All subjects in Cohorts A and B with available MRD status data.

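### MRD-negativity rates are divided by subjects with an available MRD result, not by all randomized subjects, and the plan does not say whether a Screening result is enough

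*SAP*

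**What the plan says.** The MRD paragraph of SAP 7.5 sets the population: "Analyses of MRD status will be based on all evaluable MRD subjects and performed at each sensitivity level". SAP 6.3 defines it: "All MRD Evaluable Subjects: All subjects in Cohorts A and B with available MRD status data". One set is defined for two assays, and neither a timepoint nor an assay is named.

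The opening of SAP 7.5 gives a different general rule for efficacy, "all randomized MM subjects for nivolumab/daratumumab cohorts", and the ORR definition in SAP 4.2.2 divides by the "number of randomized subjects in nivolumab/daratumumab cohort".

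Two passages point towards on-study results. SAP 7.5 states that "Cumulative MRD negativity rates will be tabulated at the first on-study assessment". In SAP 4.2.2, first and best negative status must be "recorded between the date of first dose and the date of objectively documented progression or the date of subsequent therapy, whichever occurs first".

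Protocol 5.4.1.1 requires a molecular MRD sample at Screening but no cytometry MRD sample then. The first on-study aspirate for both is at Cycle 4 Day 1, or at VGPR or better if that comes earlier. Confirmed progression before Cycle 4 also triggers an aspirate, and the medical monitor is to be contacted if a sample is not collected.

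For planning, the protocol synopsis gives exact intervals for "target MRD-target negativity rates ranging from 10% to 30% with sample size of 20 or 40 in a cohort". SAP Section 5 gives lower bounds of 11.9% (30% of 20 subjects) and 9.1% (20% of 40) and says this "compares favorably to historical MRD-target negativity rate of 8% in the target population".

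**The concern.** A Screening result can never add a negative, because the window for negative status opens at first dose. It may or may not add a subject to the denominator. If it does, the molecular denominator is close to everyone randomized. If it does not, these subjects drop out:

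- those who die or withdraw before the first on-study aspirate;
- those never treated;
- those whose aspirate the investigator judges unsafe (protocol 5.4.2 lets them continue therapy);
- those with a dry tap, where the substitute biopsy serves disease assessment only.

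For cytometry taken on its own the restricted denominator is certain, since there is no Screening sample. If SAP 6.3 is read as one set for both assays, a molecular Screening result could put a subject into the cytometry denominator too. Two analysts could follow the SAP and report different rates from the same data.

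The stakes are limited. MRD is a secondary endpoint (protocol 8.3.2.1), although protocol 5.4.1.1 is headed as the primary efficacy assessment. There is no MRD test or decision rule. What is at risk is the reported rate and how it reads beside the historical 8%, a comparison planned on full arms of 20 and 40.

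**Working it through.** **Inputs.** Cohort B has about 60 subjects randomized 2:1, so ND 40 and D 20 (SAP Section 5). The planning cases are 8/40 and 6/20, and the comparator is 8%. Intervals are two-sided 95% exact (Clopper-Pearson). Two quantities are not in the documents and are assumed: *d*, the share of an arm with no on-study result (10% and 20%), and *f*, how often those subjects are negative relative to subjects with a result (0, 0.5 and 1).

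**The plan's own figures.** 6/20 gives 11.89% to 54.28% and 8/40 gives 9.05% to 35.65%. These match the stated lower bounds of 11.9% and 9.1%, with the full planned arms as denominators.

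**Overstatement of the evaluable-only rate.** If the rate among subjects with a result is p, the rate over the whole arm is p(1 − d) + p·f·d. The ratio of evaluable to true rate is therefore 1/(1 − d + d·f).

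| d | f = 0 | f = 0.5 | f = 1 |
|---|---|---|---|
| 10% | 1/0.90 = 1.11 | 1/0.95 = 1.05 | 1.00 |
| 20% | 1/0.80 = 1.25 | 1/0.90 = 1.11 | 1.00 |

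**The planning cases with a reduced denominator** (lower limit in brackets):

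| Negatives | Full arm | 10% without a result | 20% without a result |
|---|---|---|---|
| 8 in ND | 8/40 = 20.0% (9.1%) | 8/36 = 22.2% (10.1%) | 8/32 = 25.0% (11.5%) |
| 6 in D | 6/20 = 30.0% (11.9%) | 6/18 = 33.3% (13.3%) | 6/16 = 37.5% (15.2%) |

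**Reading against 8%.** Take a lower limit above 8% as an informal yardstick.

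- ND: 7/40 gives 7.34% and 8/40 gives 9.05%, so 8 negatives are needed. 7/36 gives 8.19% and 7/32 gives 9.28%, while 6/32 gives 7.21%, so 7 are enough at either reduced size.
- D: 5/20, 5/18 and 5/16 give 8.66%, 9.69% and 11.02%; 4/20, 4/18 and 4/16 give 5.7%, 6.4% and 7.3%. Five are needed throughout, so the D arm does not change at these shares.

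**If a Screening result counts** and all 40 ND subjects have one, the denominator stays at 40 and nothing changes.

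**Effect of the all-randomized rate.** Counting a missing result as not negative gives (1 − d)/(1 − d + d·f) of the true rate. At f = 0 this is 1.00. At f = 0.5 it is 0.95 (d = 10%) or 0.89 (d = 20%), and at f = 1 it is 0.90 or 0.80.

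**The case against.** The strongest reply is that this is a prespecified choice. SAP 6.3 names an MRD-evaluable set and SAP 7.5 assigns it, and a specific rule may override a general one. That is right, and the objection here is to the choice and its loose definition, not to a contradiction.

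The 8% comparison is also informal. The plan sets no rule that the lower limit must exceed 8%, visibly plans no interval for the MRD rate itself, and says the trial is not powered for testing. In ND the reading changes only at exactly 7 negatives for the shares shown. This stands, so the threshold result is an illustration and not a broken decision rule.

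The size is assumed throughout. Mandatory aspirates, the sample at early confirmed progression and the medical-monitor contact all limit *d*. They do little for early deaths, withdrawals or unsafe procedures.

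Two further points stand. The protocol synopsis lists MRD negativity for all treated subjects and plans for about 60 treated, so an all-randomized denominator is not strictly the protocol's. It is, however, the SAP's own convention for ORR in these cohorts. Also, parts of both documents are redacted, and SAP Section 8 invokes standard imputation and counting rules that are not reproduced. The absence of a missing-result rule can be asserted only for the visible text.

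Finally, counting missing as not negative has its own downward bias. That is a reason to report both rates.

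**Conclusion.** The concern holds and is worth fixing before analysis. The MRD denominator departs from the randomized population used for ORR and from the full arms behind the planning bounds, and it is not defined tightly enough to give one answer. On the on-study reading the rate is overstated by up to 1.11-fold at 10% missing and 1.25-fold at 20%. Those maxima require that no subject without a result was negative. The overstatement shrinks to nothing as *f* approaches 1, as *d* approaches 0, or if Screening results confer evaluability on everyone. The actual missing share is unknown. Because MRD is secondary and descriptive, the consequence is a possibly inflated and non-reproducible reported rate, not a wrong trial decision.

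**What to change.** In SAP 7.5, make the main MRD-negativity rate, for each assay, the number negative at 10^-5 within the SAP 4.2.2 window divided by all subjects randomized to the arm. Count no on-study result as not negative, and give an exact 95% interval. Keep the evaluable analysis as supportive, and redefine the set in SAP 6.3 as subjects with at least one post-baseline result for the assay concerned. Tabulate the number with no result by arm, assay and reason, including subjects never treated.

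The cost is SAP wording in two sections, a main and a supportive rate per assay, and one table; no new samples are needed. The main rate will be below the evaluable rate by 10% of its value at d = 10% and 20% at d = 20%, and it is conservative if some missing subjects were in fact negative. The supportive rate shows the other end of the range.

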## **7.6 Safety**

Safety summary tables will be generated for all treated subjects. Listings will include all available data.

### **7.6.1 Death**

See CORE Safety SAP.

**7.6.2      *Serious Adverse Events***

See CORE Safety SAP.

**7.6.3      *Adverse Events Leading to Discontinuation of Study Therapy***

See CORE Safety SAP.

**7.6.4      *Adverse Events Leading to Dose Modification***

See CORE Safety SAP.

**7.6.5      *Adverse Events***

See CORE Safety SAP.

**7.6.6      *Select Adverse Events***

See CORE Safety SAP.

**7.6.7      *Immune Modulating Medication***

See CORE Safety SAP.

**7.6.8      *Multiple Events***

See CORE Safety SAP.

**7.6.9      *Laboratory Parameters***

See CORE Safety SAP.

**7.6.10     *Vital Signs***

See CORE Safety SAP.

**7.6.11     *Immunogenicity Analysis***

Immunogenicity analyses will be performed separately for Nivolumab ADA Evaluable Subjects.  
See CORE Safety SAP.

**7.6.12     *Pregnancy***

See CORE Safety SAP.

**7.6.13     *Clinical Safety Program (CSP)***

See CORE Safety SAP.

## 7.7 Pharmacokinetics

Summary statistics will be tabulated for the pharmacokinetic parameters of nivolumab when administered as a single agent, nivolumab and ipilimumab when administered in combination, nivolumab and lirilumab when administered in combination and nivolumab when administered in combination with daratumumab by treatment arm and dose level in each study week as appropriate. To describe the dependency on dose, scatter plots of Cmax and AUC(0-T) versus dose will be provided for each day measured. To assess attainment of steady state, plots of Cmin versus time will be provided. Pharmacokinetic concentrations from all samples will be listed (including the limited samples collected but not included in parameter calculations), and may be used in combination with other studies for exposure-response or population pharmacokinetic modeling, which will be part of a separate report.

[REDACTED]

[REDACTED]

[REDACTED]

[REDACTED]

[REDACTED]

[REDACTED]

[REDACTED]

[REDACTED]

[REDACTED]

[REDACTED]

[REDACTED]

[REDACTED]

[REDACTED]

[REDACTED]

[REDACTED]

[REDACTED]

[REDACTED]

[REDACTED]

[REDACTED]

[REDACTED]

[REDACTED]

[REDACTED]

[REDACTED]

[REDACTED]

